1.5.2. Rationale for the Voxelotor Dose to be Evaluated in Part B

Based on the single dose safety and preliminary PK of voxelotor in adolescents, 900- and 1500-mg doses have been selected to be evaluated in Part B of GBT440-007. The doses of voxelotor 900 and 1500 mg to be evaluated in pediatric participants in Part B of GBT440-007 are the same as the doses selected to be evaluated in GBT440-031 (Group 1, Phase 3 study). The doses of voxelotor 900 and 1500 mg to be evaluated in Study GBT440-031 are based on the 20% to 30% optimal treatment target for efficacy based on genetic data (HbS/ hereditary persistence of fetal hemoglobin [HPFH]), genetic data for safety (high affinity Hb mutations that are well

tolerated with Hb oxygen affinity corresponding to Hb modification of 30% or higher), and on response and safety data from the Phase 1/2 study GBT440-001. To achieve optimal efficacy, HbS polymerization and sickling should be inhibited at all times, therefore the efficacy target of 20% to 30% is based on the minimum occupancy target based on minimum drug concentration (C_{min}) voxelotor blood levels.

- Individuals with the deletional form of HbS/HPFH have HbF levels in the range of approximately 20% to 30% with no clinical manifestations of SCD (Ngo, 2012). Because in vitro experiments have shown that voxelotor modified Hb delays HbS polymerization with similar potency to hemoglobin fetal (HbF), 20% to 30% is a reasonable target for voxelotor Hb occupancy.
- The target range of 20% to 30% Hb modification is supported by treatment response data from study GBT440-001. Participants with SCD treated in study GBT440-001 at 700 mg, 900 mg and 1000 mg per day achieved Hb occupancy in the range of approximately 20% to 30%. Hematologic responses (on hemolysis markers and sickle cell counts) were seen at all dose levels tested, and a dose response was evident for some hemolysis measures (bilirubin and reticulocytes). The greatest Hb increase was seen in cohorts dosed for 90 days. Participants who achieved > 20% Hb occupancy showed an improved hematologic response compared to those who did not. In addition, individual participants with dose reductions gave evidence of improved response while maintaining Hb occupancy > 20%.
- Exposure response analysis and PK/PD modeling of GBT440-001 data demonstrate a highly significant and liner relationship between exposure and improvement in hemolysis measures (ie, at the doses tested, a plateau on improvement in hemolysis measures has not been reached)
- Modeling and simulation predictions based on data derived from GBT400-001 for the hemolysis measures, indirect bilirubin, reticulocyte counts, LDH and Hb for voxelotor doses of 900 and 1500 mg are summarized in [Table 1](#). To date, doses up to 1000 mg have been evaluated clinically. Since 1500 mg has not been previously evaluated, the exposure response analysis and simulations were based on an E_{max} model.

Modeling and simulation based on adult data predict that voxelotor 900- and 1500-mg doses will achieve voxelotor blood concentrations at C_{min} in the median participant equivalent to Hb modification of 16% (2.5th to 97.5th percentile 7% to 31%) and 26% (2.5th to 97.5th percentile 12% to 52%), respectively. Based on this prediction, 25% of participants at 900 mg, and 76% of participants at 1500 mg, will maintain > 20% Hb occupancy, respectively.

Table 1: Simulated Hemolysis Measures Outcomes Based on Data in Adult Participants (% Change from Baseline) for Voxelotor 900 and 1500 mg

Hemolysis Measure	Dose of Voxelotor	
	900 mg	1500 mg
Bilirubin (%)	-47 (27–84)	-66 (51–78) ^a
Reticulocytes (%)	-53 (30–93)	-84 (61–94) ^a
LDH (%)	-30 (17–54)	-64 (37–84) ^a
Hemoglobin (%)	11.9 (6.7–21.1)	— ^b
Hemoglobin (change from baseline) ^c	1.06 (0.60–1.9)	— ^b

Abbreviation: LDH, lactate dehydrogenase.

Note: Values represent median (2.5th to 97.5th percentiles).

^a Based on E_{max} model.^b The E_{max} model underestimated the change in Hb and cannot be used and the linear model may overestimate.^c Based on a Baseline Hb of 9 g/dL.

A population (POP) PK model was developed for adolescents using the same model structure (2-compartment model with first order absorption) as the adult POP PK model. Voxelotor PK parameters were estimated and compared to the adult values. Overall, all major (eg, clearance, volume) PK parameters for the whole blood voxelotor are projected to be similar (Table 2) between adult and adolescent participants indicating that there is no significant difference between these two participant populations. Based on these data, the same doses are recommended for adolescents and adults.

Table 2: Parameter Estimates From the Whole Blood Voxelotor Population PK Model (Adults Versus Adolescents)

PK Parameters	Voxelotor Whole Blood Adults (RSE %)	Voxelotor Whole Blood Adolescents (RSE %)
CL (L/h)	0.43 (5)	0.37 (13)
V (L)	21.4 (6)	15 (17)
KA (1/h)	0.34 (13)	0.19 (30)
Proportional error (%)	28 (8)	70 (8)
Additive error (ng/mL)	4.6 (41)	-

Abbreviations: CL, clearance; KA, absorption rate constant; RSE, relative standard error; V, volume of distribution.

1.5.3. Rationale for the Voxelotor Dose to be Evaluated in Children 4 to 11 Years Old in Part C and Children 6 Months to < 4 Years Old in Part D

Participants (aged 12 to < 18 years) in Part B received 1500 mg. Currently, participants in Part C are receiving voxelotor 1500 mg once daily or, if younger than 12 years of age or with weight < 40 mg, a 1500-mg equivalent once daily using a weight-based design (see [Table 3](#)).

Participants in Part D will receive a 1500-mg equivalent once daily using a weight-based design (see [Table 3](#)).

Table 3: Voxelotor Weight-Based Doses Determined for Pediatric Participants

Population	Voxelotor Doses
	1500 mg-Equivalent Adult Dose
5 to < 10 kg	400 mg
10 to < 20 kg	600 mg
20 to < 40 kg	900 mg
≥ 40 kg	1500 mg

The doses of voxelotor to be evaluated in Parts C and D of this study are based on targeting clinical efficacy in adult and adolescent participants, combined with population PK (PPK) modeling, physiologically based PK (PBPK) modeling, and allometric scaling and are expected to provide exposures of voxelotor equivalent to exposures observed in adults and adolescents (Study GBT440-031) and adolescents (Study GBT440-007) following multiple doses of 1500 mg.

To estimate appropriate doses to be evaluated in pediatric participants (6 months to < 12 years) with SCD, multiple doses of voxelotor were simulated by weight group (10 to < 20 kg and 20 to < 40 kg). The dose simulations were based on a voxelotor whole blood PPK model, including data from adults, adolescents, and children age 6 to 11 years old. The model used the same model structure (2-compartment model with first-order absorption) as the adult PPK model. The clearance (CL) and central volume (Vc) were scaled allometrically (exponents of 0.75 for CL and 1 for Vc) based on participant weights sampled from age-stratified normal distributions for children with homozygous SCD ([Thomas, 2000](#)). Summary exposure metrics (AUC, C_{max,ss}, and minimum drug concentration [C_{min,ss}]) in children (9 months to < 12 years) were compared to the interquartile range of exposures simulated for the equivalent dose in adolescent participants.

Weight-based groups were identified to target median exposures within the adolescent interquartile range. Based on simulations in the pediatric population, doses of 400, 600, and 900 mg, respectively, are supported to provide exposures similar to adolescent participants at 1500 mg. Participants with weights > 40 kg will receive the same dose as adolescent or adult participants.

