--	--

	
Approximately 30 pediatric participants will be enrolled.
 
At least 10 participants must be 6 months to < 2 years of age.
Dose	
Part A: Voxelotor 600 mg (two 300 mg capsules or tablets) single dose.
 
Part B: Voxelotor 900 mg (administered as three 300 mg capsules or tablets) or 1500 mg (administered as five 300 mg capsules or tablets) once daily (QD) for 24 weeks.
 
Part C: Participants who are between 12 and 17 years of age will receive voxelotor 1500 mg/day as dispersible tablets or powder for oral suspension for 48 weeks.
 
Participants who are between 4 to 11 years of age will receive voxelotor 1500 mg/day EQUIVALENT based on body weight as dispersible tablets or powder for oral suspension for 48 weeks (see Table 3).
 
Part D: Participants will receive voxelotor 1500 mg/day EQUIVALENT based on body weight as powder for oral suspension for 48 weeks (see Table 3). If powder for oral suspension is not available, dispersible tablets will be used.

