3.1.3. Part C (Multiple-Dose Administration)

The Study Schematic for Part C is provided in [Figure 4](#). Up to 50 pediatric participants who are 4 to 17 years of age with SCD will be enrolled.

[figure not shown]
- At least 30 participants must have a TCD velocity ≥ 140 and < 200 cm/sec by nonimaging TCD (≥ 125 and < 185 cm/sec by TCDi) upon Screening AND
- At least 20 participants must be between 4 to 11 years of age

Participants' age will be the age at the time of the assent/consent.

During the 35-day screening period, participants will undergo TCD assessment and those who meet the criteria for TCD and the rest of the study eligibility criteria will be eligible for treatment and will receive multiple doses of voxelotor (up to 48 weeks).

Following completion of study treatment in Part C, eligible participants may be given the option to enroll in an open-label extension study (under a separate protocol) to receive voxelotor.

Figure 4: Part C Multiple-Dose Schema

Part C: Potential Modification

To further characterize a potential effect on TCD data for those participants who have a TCD velocity ≥ 140 and < 170 cm/sec by nonimaging TCD (≥ 125 and < 155 cm/sec by TCDi) upon screening, approximately 20 participants may be added with a TCD velocity that falls within this range, depending on the emerging data. In this event, Part C will contain up to 70 pediatric participants.

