5.3. Clinical Assessments

Screening assessment must be conducted within 28 days prior to initiation of dosing for Part A, and within 35 days prior to initiation of dosing for Parts B, C, and D. Laboratory assessments, vital signs and physical examinations conducted on Day 1 predose may be conducted on Day -1. Refer to [Appendix 1](#), [Appendix 3](#), [Appendix 5](#), and [Appendix 7](#) for additional details.

Clinical assessments, including weight, vital signs, ECGs, AEs, and concomitant medications will be conducted at specified time points during the study (refer to [Appendix 1](#), [Appendix 3](#), [Appendix 5](#), and [Appendix 7](#)). Vital signs data to be collected include supine systolic and diastolic blood pressure, pulse rate, respiration rate and temperature (in °C). 12-lead ECGs will be collected in triplicate. Any other medical condition present at baseline should be followed during the study, and a change from the baseline status (intensity or frequency) should be reported as an AE if deemed clinically significant by the Investigator (refer to Section 9).

Height and weight will be recorded as outlined in [Appendix 1](#), [Appendix 3](#), [Appendix 5](#), and [Appendix 7](#). There is no weight restriction for Parts A, B, or C of the study. Height (in centimeters) and weight (in kilograms) should be measured with the participant's shoes off. Head circumference will be recorded in Part D as outlined in [Appendix 7](#).

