7.1.2. Part C

Participants who are between 12 and 17 years of age will receive voxelotor, 1500 mg/day as dispersible tablets or powder for oral suspension.

Participants who are between 4 to 11 years of age will receive voxelotor, 1500 mg/day EQUIVALENT based on body weight as dispersible tablets or powder for oral suspension. The participant's weight at screening will be used to determine the initial treatment dose ([Table 3](#)).

Details regarding preparation for administration are provided in the Pharmacy Manual (provided separately). Detailed instructions will be provided to participants and their caregiver/legal guardian prior to the first dose of study drug.

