7.1.5. Formulation

Voxelotor Capsules: Voxelotor 300 mg capsules contain granulation consisting of voxelotor drug substance along with several formulation excipients in Swedish orange, opaque, size 0, Hypromellose capsules. All the excipients used for the formulation are GRAS (Generally recognized as safe) materials and are also FDA IIG (Inactive Ingredients Guide) listed.

Voxelotor Tablets: The voxelotor 300 mg tablets contain voxelotor drug substance along with several formulation excipients. All the excipients used for the formulation are FDA Inactive Ingredients Database (IID) listed and compliant with European Regulations.

Voxelotor Dispersible Tablets: Voxelotor will be supplied as 100 or 300 mg dispersible tablets.

Voxelotor Powder for Oral Suspension: Voxelotor will be supplied as 300-, 400-, 600-, or 900-mg powder for oral suspension packaged as stick packs.

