8. DOSAGE AND TREATMENT ADMINISTRATION

8.1. Treatment Regimen

In Part A, participants will receive a single oral dose of voxelotor 600 mg (two 300 mg capsules or tablets).

In Part B, participants will receive voxelotor administered each day for 24 weeks (168 days). Voxelotor will be administered as 300 mg capsules or tablets.

In Part C, participants will receive voxelotor administered each day for 48 weeks (336 days). Participants who are between 12 to 17 years of age will receive voxelotor, 1500 mg/day as dispersible tablets or powder for oral suspension. Participants who are between 4 to 11 years of age will receive voxelotor 1500 mg/day EQUIVALENT as dispersible tablets or powder for oral suspension based on body weight. Either dispersible tablets (100 or 300 mg) or powder for oral suspension (300, 400, 600, or 900 mg) will be used based on [Table 3](#).

In Part D, participants will receive voxelotor administered each day for 48 weeks (336 days). Participants will receive voxelotor 1500 mg/day EQUIVALENT as powder for oral suspension based on body weight. Voxelotor powder for oral suspension (300, 400, 600, or 900 mg) will be used based on [Table 3](#). If powder for oral suspension is not available, dispersible tablets will be used and will be supplied as 100 or 300 mg tablets.

Instructions for administration of study drug for capsules (Part B):

- Voxelotor will be self-administered by the participant in the morning. When necessary, a parent or guardian may be present to assist with this process.
 - except on study visit days when the participant must not take study drug at home. It will be administered at the site after completion of appropriate assessments.
- Participants should take voxelotor with water or other non-alcoholic beverage.

Instructions for administration of study drug as dispersible tablets or powder for oral suspension (Parts C and D):

- Details regarding the dosing preparation and oral administration of the dispersible tablets or powder for oral suspension are provided in the Pharmacy Manual (provided separately).
- For younger participants, voxelotor administration should be supervised by a parent or guardian. Detailed instructions will be provided to participants and their caregivers/legal guardians prior to the first dose of study drug.

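### Part C, ages 12–17: the protocol gives two different daily doses to participants under 40 kg, and Table 6 states its dose reduction without a milligram amount for the Part C formulations

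*Protocol*

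**What the plan says.** **Starting dose.** Section 1.5.3 of the protocol describes current Part C dosing as a fixed 1500 mg each day, with an exception that refers to Table 3: "if younger than 12 years of age or with weight < 40 mg, a 1500-mg equivalent once daily using a weight-based design". In that table, 20 to < 40 kg corresponds to 900 mg, and 40 kg or more to 1500 mg.

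The dosing passages split by age only:

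- Synopsis, Dose: "Participants who are between 12 and 17 years of age will receive voxelotor 1500 mg/day as dispersible tablets or powder for oral suspension".
- Section 7.1.2: "Participants who are between 12 and 17 years of age will receive voxelotor, 1500 mg/day as dispersible tablets or powder for oral suspension".
- Section 8.1: "Participants who are between 12 to 17 years of age will receive voxelotor, 1500 mg/day as dispersible tablets or powder for oral suspension". After the 4–11 rule it has a further sentence, which cites Table 3 and names no age group: "Either dispersible tablets (100 or 300 mg) or powder for oral suspension (300, 400, 600, or 900 mg) will be used based on".
- Section 8.2.1 makes the same age split.

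On eligibility by weight, Section 5.3 says: "There is no weight restriction for Parts A, B, or C of the study".

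**Dose reduction.** Section 8.2.2 applies Tables 6 and 7 to ages 12–17 in Parts B and C. Every reduction in Table 6, including those for ALT rises, is expressed as a single tablet with no mg figure. Table 7, for rash only, equates one capsule or tablet with 300 mg. Table 8 lists reduced doses in mg, but it belongs to Section 8.2.3, which covers ages 4–11 in Part C and all of Part D. On the Part C tablets, Section 7.1.5 says: "Voxelotor will be supplied as 100 or 300 mg dispersible tablets". The powder comes in stick packs of 300, 400, 600 or 900 mg.

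**The concern.** The word joining the two conditions in Section 1.5.3 is *or*, so weight alone brings a participant aged 12 or over under Table 3. Under the synopsis and Sections 7.1.2, 8.1 and 8.2.1, weight has no bearing at that age. Two sites relying on different sections could give the same adolescent different daily doses for 48 weeks.

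Three things follow.

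- Section 8.2.3 adjusts dose for weight change only at ages 4–11 and in Part D. An adolescent started by weight who then passes 40 kg has no stated rule.
- Part C results are summarized by age group (Protocol Section 10.3; Part C SAP Section 7), and the exposure summary (Part C SAP Section 7.3.1) covers duration, missed doses and reductions, not the mg dose. A 12–17 group that mixed 900 and 1500 mg would not show in these summaries.
- After a drug-related adverse event or an ALT rise, Table 6 does not tell a Part C site how many mg to remove.

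**Working it through.** The plan gives no figure to reproduce. The check sets the passages side by side for one case: Part C, aged 12–17, weighing 20 to < 40 kg. It reads the printed unit in Section 1.5.3 as kg, because 40 kg is a Table 3 cut-off.

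| Source | Rule applied | Daily dose |
|---|---|---|
| Section 1.5.3 with Table 3 | under 12 years or under 40 kg: by weight | 900 mg |
| Synopsis | age 12–17 | 1500 mg |
| Section 7.1.2 | age 12–17 | 1500 mg |
| Section 8.1 | age 12–17, then strengths chosen from Table 3 | 1500 mg as stated; the Table 3 sentence has no age limit |
| Section 8.2.1 | age 12–17 | 1500 mg |

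**Can the case occur?** Yes. Section 5.3 sets no weight limit for Part C.

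**Size of the dose difference.** 1500 − 900 = 600 mg, and 1500/900 = 1.67. Under the protocol's own relation in Section 1.5.1, AUC = Dose/CL, a participant with a given clearance has the same 1.67-fold ratio in exposure.

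**How many participants.** Section 3.1.3 caps Part C at 50 and adds: "At least 20 participants must be between 4 to 11 years of age". So at most 50 − 20 = 30 are aged 12–17, or 70 − 20 = 50 with the potential modification. The share under 40 kg is not given, so the number affected lies between 0 and 30 (or 0 and 50). The upper ends would require every adolescent to weigh under 40 kg.

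**Table 6 step, read literally.**

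| Starting dose | 100 mg tablet | 300 mg tablet | Powder |
|---|---|---|---|
| 1500 mg | 100/1500 = 6.7% | 300/1500 = 20% | not defined |
| 900 mg | 100/900 = 11.1% | 300/900 = 33.3% | not defined |

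In Part B the capsules and tablets are all 300 mg, so the wording is unambiguous there. In Part C it is not, and powder is not a rare case: Appendix 5 calls for all participants to have a transition visit within 30 days of powder becoming available.

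Table 8 does not settle the step. It is written for other participants, and its steps are not uniform: from 1500 mg the first is 1500 − 1200 = 300 mg, while the second step in the 20 to < 40 kg band is 600 − 400 = 200 mg.

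**The case against.** Section 1.5.3 is rationale text in the Introduction, under a heading about ages 4–11 in Part C and about Part D. The synopsis, Section 7.1.2 and Section 8.2.1 agree with one another, and Section 8.1 states 1500 mg for ages 12–17 outright before its Table 3 sentence, which follows directly on the 4–11 rule. A site would normally dose from those sections, and from the Pharmacy Manual, which is not available here. The number affected may be zero. Both 900 and 1500 mg were given to ages 12–17 in Part B, and Section 3.5.2 records that the DSMB supported continuing both. For Table 6, the 300 mg in Table 7 makes that step a natural inference for tablets, since 900 and 1500 are whole multiples of 300. Dose modifications must also be notified to the Medical Monitor within 72 hours.

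Much of this stands. It lowers the chance that sites actually diverged, and it makes Table 6 a matter of wording more than of conflict. It does not remove the main point. The sentence in Section 1.5.3 reports how Part C participants are being dosed. Either that report is wrong, or some adolescents were dosed differently from Sections 7.1.2 and 8.1, and the documents do not say which. The Part B experience is not reported for participants under 40 kg. Notifying the Medical Monitor afterwards does not define the amount to remove, and Table 7 covers neither powder nor events other than rash.

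**Conclusion.** The concern holds. For a Part C participant aged 12–17 and weighing 20 to < 40 kg, the protocol gives both 900 and 1500 mg daily, a 1.67-fold difference, and no passage resolves it. This must be corrected even if few participants are affected, because it concerns a child's daily dose. The finding assumes that the printed unit stands for kg and that the participant weighs at least 20 kg. The number affected is unknown and may be zero.

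The Table 6 wording is independent and secondary: settling the starting dose would not define the reduction step. It affects all Part C participants aged 12–17, whatever their weight.

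**What to change.** - Reconcile Section 1.5.3 with the synopsis and Sections 7.1.2, 8.1 and 8.2.1, so that one rule governs ages 12–17 under 40 kg. Say whom the Table 3 sentence in Section 8.1 covers, and correct mg to kg.
- State the Table 6 reduction step in mg for each Part C formulation, including powder, and reconcile it with Table 7.
- Write to sites with the clarified text.
- Check dispensing and CRF records for the dose actually given to any Part C participant aged 12–17 and under 40 kg.

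The clinical team decides which dose rule and which reduction step apply; this review takes no position on either. The cost is a protocol clarification or short amendment, a site letter and a check of existing records, with no added participants or procedures.

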1.6. Risk Assessment

Based on the mechanism of action of voxelotor and findings in the nonclinical safety toxicology studies, voxelotor could cause tissue hypoxia. In GLP toxicology studies, rats dosed for 28 days with ≥ 250 mg/kg/day demonstrated increased erythropoietin and red cell mass (hematocrit [Hct], RBC, or Hb) with extramedullary hematopoiesis and bone marrow hypercellularity. These findings are consistent with expected physiologic compensation to hypoxia, were well tolerated in the rat, were not considered adverse, and were reversible.

In prior clinical experience with other agents, no adverse reactions related to tissue hypoxia were reported at the highest tested doses of tucarsesol administered in either healthy participants (maximum 40% Hb-modification) or participants with SCD (maximum 24% Hb -modification), or BW12C infusions in either healthy participants (maximum 40% Hb -modification) or participants with SCD (23% Hb modification) (Arya, 1996 ; Keidan, 1986; Nicholls, 1989; Rolan, 1995). Appropriate acute and chronic compensatory physiologic responses to tissue hypoxia were observed, including an increase in heart rate during moderate exercise and a slight increase in reticulocyte counts at high doses (Nicholls, 1989; (Rolan, 1995; Rolan, 1993). Importantly, healthy participants were well-compensated both at rest and at near maximal exercise with little change in resting heart rate (Nicholls, 1989). Potential tissue hypoxia can be monitored by hematology laboratory studies, erythropoietin levels, and cardiovascular parameters.

Gastrointestinal effects (primarily emesis, and soft or liquid feces) were observed in all species and were dose-limiting in dogs and monkeys. Gastrointestinal erosions, ulcers, or epithelial hyperplasia were observed at high doses in rats.

The most common AEs with an incidence of at least 20% were headache and diarrhea (Vichinsky, 2019). The majority of these TEAEs were Grade 1 or 2 in severity. The percentages of participants who had a Grade 3 event, a serious adverse event (SAE), and/or treatment discontinuation due to an AE did not differ substantially among the 3 treatment arms (1500 mg voxelotor, 900 mg voxelotor, or placebo).

In addition, the decline in erythropoietin levels suggest an improvement in oxygen delivery either by increase in hemoglobin or improvement in microvascular blood flow, or both (Vichinsky, 2019; Howard, 2019).

